19.1 List of endpoints

Group	Endpoint	Treatment Phase	Follow-up (integrated)	Reference
		Baseline to LOCF1	Baseline to LOCF2	
Trial Subjects	Disposition	Descriptive	Descriptive	12
	Protocol Deviations	Descriptive	Descriptive	12.1
Demographics and other baseline characteristics	Demographics	Descriptive	Descriptive	13.1
	Medical History	Descriptive	Descriptive	13.2
	Baseline Characteristics	Descriptive	Descriptive	13.3
Concomitant Medication and procedures	Previous medication and procedures	Descriptive	Descriptive	14
	Concomitant medication and procedures	Descriptive	Descriptive	14
	Pain medication	Descriptive	Descriptive	14
Exposure and treatment compliance	Exposure	Descriptive	Descriptive	15
	Compliance	Descriptive	Descriptive	15
Efficacy	Change from baseline in average cartilage thickness in the total femorotibial joint as evaluated by MRI in the target knee	Primary: Descriptive Analysis Sensitivity analysis (PP) Model check	Exploratory: Descriptive Analysis Model check	16.1
	WOMAC total score in the target knee at baseline and post- baseline	Secondary endpoint Descriptive Analysis Sensitivity analysis (PP) Subgroup analysis	Exploratory: Descriptive Analysis Model check	16.2
	WOMAC sub scores in the target knee at baseline and post- baseline	Secondary endpoint Descriptive Analysis Sensitivity analysis (PP) Subgroup analysis	Exploratory: Descriptive Analysis Model check	16.2

Group	Endpoint	Treatment Phase	Follow-up (integrated)	Reference
		Baseline to LOCF1	Baseline to LOCF2	
	20-meter WALK test	Secondary endpoint Descriptive Analysis	Descriptive	16.2
	PGA	Secondary endpoint Descriptive	Descriptive	16.2
	JSW on X-ray in the target knee at screening or baseline – and post-treatment	Secondary endpoint Descriptive Analysis Sensitivity analysis (PP) Subgroup analysis	Exploratory: Descriptive Analysis Model check	16.2
	Regional Average Cartilage thickness on MRI	Secondary endpoints Descriptive Analysis	Descriptive	16.2
	Total and Regional Cartilage Volume	Secondary endpoint Descriptive Analysis	Descriptive	16.2
PK	Synovial fluid levels of sprifermin/FGF-18	Descriptive	NA	16.3
	Serum levels of sprifermin/FGF-18	Descriptive	NA	16.3
PK/Safety	Occurrence of antibodies	Descriptive	NA	16.3 and 17
Other endpoints	OMERACT-OARSI score for the target knee	Descriptive Analysis	Descriptive	16.5
	PGIC	Descriptive	Descriptive	16.5
	KOOS Qol Score	Descriptive	Descriptive	16.5
	KOOS Symptom index	Descriptive	Descriptive	16.5
	MOS SF-36 Score	Descriptive	Descriptive	16.5
	NRS Pain Score for the target and contralateral knee	Descriptive	Descriptive	16.5
	Pain in other joints	Descriptive	Descriptive	16.5

Sprifermin (AS902330) Statistical Analysis Plan (Final) EMR700692 $_006-v1.0$

Group	Endpoint	Treatment Phase	Follow-up (integrated)	Reference
		Baseline to LOCF1	Baseline to LOCF2	
	ICOAP Score for the target knee	Descriptive	Descriptive	16.5
	Semi quantitative MRI endpoints (WORMS/BLOKS) for the target knee	Descriptive Analysis	Descriptive	16.5
	Biomarkers	Descriptive for PGX and biochemical biomarkers. Other biomarkers will be defined in the BSAP [to be finalized prior to unblinding]		16.4
	Modeling	Will be defined in Modeling SAP		
	Subgroup analysis (including biomarkers subgroups)	Descriptive Analysis		16.4 and 16.5
	Additional analyses (changes and in addition to those specified in the protocol)	Descriptive Analysis	Descriptive	16.5
Safety	Adverse Events	Descriptive	Descriptive	17.1
	Death	Descriptive	Descriptive	17.2
	AIR	Descriptive Analysis	NA	17.2.3
	Clinical laboratory parameters	Descriptive	Descriptive	17.3
	Vital signs	Descriptive	Descriptive	17.4
	Physical Examination	Descriptive	Descriptive	0
	ECG	Descriptive	Descriptive	17.6

19.2 List of permitted pain medication

19.3 Handling of medication timing

19.3 Handling of medication timing				
	CMstart	CMstart	CMstart Year	CMstart missing
	Year/Month/day	Year/Month		
CMend Year/Month/day	(1) if CMstart Year/month/day > DoLD year/month/day => CM is Post; (2) else if CMend Year/month/day < DoFD year/month/day => CM is Previous; (3) else CM is Concomitant	(1) if CMstart Year/month > DoLD year/month => CM is Post; (2) else if CMend Year/month/day < DoFD year/month/day => CM is Previous; (3) else CM is Concomitant	(1) if CMstart Year > DoLD year => CM is Post; (2) else if CMend Year/month/day < DoFD year/month/day => CM is Previous; (3) else CM is Concomitant	(1) if CMend Year/month/day < DoFD year/month/day => CM is Previous; (2) else if CMend Year/month/day >= DoFD year/month/day => CM is Concomitant
CMend Year/Month	(1) if CMstart Year/month/day > DoLD year/month/day => CM is Post; (2) else if CMend Year/month < DoFD year/month => CM is Previous; (3) else CM is Concomitant	(1) if CMstart Year/month > DoLD year/month => CM is Post; (2) else if CMend Year/month < DoFD year/month => CM is Previous; (3) else CM is Concomitant	(1) if CMstart Year > DoLD year => CM is Post; (2) else if CMend Year/month < DoFD year/month => CM is Previous; (3) else CM is Concomitant	(1) if CMend Year/month < DoFD year/month => CM is Previous; (2) else if CMend Year/month>= DoFD year/month => CM is Concomitant
CMend Year	(1) if CMstart Year/month/day > DoLD year/month/day => CM is Post; (2) else if CMend Year < DoFD year => CM is Previous; (3) else CM is Concomitant	(1) if CMstart Year/month > DoLD year/month => CM is Post; (2) else if CMend Year < DoFD year => CM is Previous; (3) else CM is Concomitant	(1) if CMstart Year > DoLD year => CM is Post; (2) else if CMend Year < DoFD year => CM is Previous; (3) else CM is Concomitant	(1) if CMend Year < DoFD year => CM is Previous; (2) if CMend Year>= DoFD year => CM is Concomitant
CMend missing	(1) if CMstart Year/month/day > DoLD year/month/day => CM is Post; (2) else if CMstart Year/month/day < =DoLD	(1) if CMstart Year/month > DoLD year/month => CM is Post; (2) else if CMstart Year/month < =DoLD year/month =>	(1) if CMstart Year > DoLD year => CM is Post; (2) else if CMstart Year < =DoLD year => CM is Concomitant	Concomitant

CMstart Year/Month/day	CMstart Year/Month	CMstart Year	CMstart missing
year/month/day	CM is		
=> CM is	Concomitant		
Concomitant			

If subject is not treated, medication flag will be always "Previous" and use planned treatment for ITT/mITT Analysis sets in TLFs. Assumption is Day of First Dose (DoFD) and Day of Last Dose (DoLD) are not missing and complete for all treated subjects.

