6.5 Concomitant Medications and Therapies

6.5.1 Permitted Medicines

Any medications (other than those excluded by the clinical trial protocol) that are considered necessary for the subjects' welfare and will not interfere with the trial medication may be given at the Investigator's discretion.

The Investigator will record all concomitant medications taken by the subject during the trial, from the date of signature of informed consent, in the appropriate section of the CRF.

Any additional concomitant therapy that becomes necessary during the trial and any change to concomitant medication must be recorded in the corresponding section of the CRF, noting the name, dose, frequency of administration, duration, and indication of each medication.

During the screening period, all analgesic medication must be withheld for 5 half-lives before the screening (Visit 1b) and baseline WOMAC assessments. Aspirin (acetylsalicylic acid) used for cardiovascular protection does not need to be withheld, nor do antidepressants used for management of OA pain or depression.

Paracetamol (acetaminophen), NSAIDs including coxibs, and tramadol may be resumed following randomization and continued as needed during the trial, except during the brief analgesic withdrawal periods prior each study visit at which WOMAC data are obtained.

During the trial, paracetamol (acetaminophen) is recommended as rescue medication for the treatment of breakthrough pain. The dosage of acetaminophen or paracetamol that the subjects will be allowed to take per day will be defined according to the standard of care in the countries where the trial will be carried out; however, the maximum dose should not exceed 1 gram per dose and 4 grams/day. Low-dose narcotics or combination products such as paracetamol/acetaminophen and oxycodone (Percocet) may be used only as needed for more severe painful episodes. Duration of opioid use is limited to 14 days per episode. If the subject requires regular narcotic analgesia to control his/her arthritis pain, s/he should not be considered for the trial.

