- 3. baseline mal-alignment in target knee (< -3 or > 3 or [-3,3] degrees)

Pain medications [classified for 3 timing groups defined in Section 14]:

- 1. Pain medications (Yes, No) any of 2, 3 or 4 defined below
- 2. Analgesics, Opiods in WHO ATC code group N02A (Yes, No)
- 3. Analgesics, Other analgesics and antipyretics in WHO ATC code group N02B (Yes, No)
- 4. Non-steroid anti-inflammatory and antirheumatic products in WHO ATC code group M01A (Yes, No)

Other subgroups:

Subgroups defined by SNPs and biochemical biomarkers cutoffs subgroups (see Section 16.4);

A listing of protocol-permitted concomitant pain medications and their respective washout times was provided in Appendix 19.2. Prior to unblinding this list may be updated.

Subgroups will be defined by individual listing prior to database lock and prior to breaking the blind for the reporting of the treatment phase.

11 General Specifications for Statistical Analyses

It is planned to perform the statistical analysis in two steps. Approximately one month after the last subject reaches day 819 of the 2-year DBPC treatment phase, the database will be partially locked, the treatment code will be un-blinded. Thereafter, complete analyses will be performed, and a detailed CTR will be written based on the data collected up to the end of the DBPC treatment phase (day 819). Long term follow-up data (from Year 2 to Year 5) will be integrated and analyzed with the DBPC treatment phase data but reported separately from the DBPC treatment phase results. Investigators, other site staff, study monitors, and subjects will remain blinded to study treatment during the extended follow-up phase as described in Section 8. X-ray and MRI readers will remain blinded to study treatment until completion of the extended follow-up phase results.

A list of endpoints according to treatment phase is provided in Appendix 19.1.

Summary Statistics

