13.3 Other Baseline Characteristics

Other Baseline Characteristics include the following variables:

- Alcohol and nicotine consumption
- Specification of target knee OA: (KL Grade 2 or 3, target knee location (Left or Right knee), medial and lateral mJSW, Anatomic axis angle (AAA) of knee alignment [in degrees calculated as 180 ANGLE, where ANGLE is the value corresponding to xmtestcd = 'ANGLE'], response to Question 1 of the WOMAC pain index at screening, and time since diagnosis
- Contralateral knee: KL Grade (0, 1, 2, 3), medial and lateral mJSW

- Pain in other joints (yes/no, and if yes, how many joints and which joints specifically)
- All other attributes defined in subgroups analysis set in Section 10.

14 Previous or Concomitant Medications/Procedures

Medication start and stop dates will be compared to the date of first dose of study medication, see appendix 20.3, to allow medications to be classified as

- (a) Previous,
- (b) Concomitant, or
- (c) Post-treatment medications.

All medications categories will be summarized and listed. Medications that start and stop prior to the date of first dose of study medication will be classified as previous medication. If a medication starts or stops on or after the date of first dose of study medication and prior to last dose, then the medication will be classified as Concomitant. Medications that start after last injection will not be considered concomitant and will be categorized as Post-treatment medications. If medication start and/or stop dates are missing or partial, the dates will be compared with the date of first dose of study medication. Medications will be assumed to be Concomitant, unless there is clear evidence (through comparison of partial dates) to suggest that the medication stopped prior to the first dose of study medication (in which case the medication will be assumed to be Previous medication) or started after last injection (in which case the medication will be assumed to be Post-treatment medication).

Pain and other medication such as NSAIDs taken in each of the three categories (a,b,c) described above will be summarized and listed. List of pain medication is attached in Appendix 19.2.

All medications will be coded using the latest version of the WhoDrug Anatomic therapeutic class (ATC) Medications using the indication or using the secondary level of the ATC code. Coding will be updated for the 5-year analysis.

Procedures will be listed only.

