- Summary Statistics by Visit and Change in WOMAC Total Score from Baseline to 2 Years, by Treatment ITT Analysis Set
- 17. Summary Statistics by Visit and Change in WOMAC Pain Sub Score from Baseline to 2 Years, by Treatment ITT Analysis Set
- 18. Summary Statistics by Visit and Change in WOMAC Function Sub Score from Baseline to 2 Years, by Treatment ITT Analysis Set
- 19. Absolute Change (ANCOVA) from Baseline up to 2 years in WOMAC Total Score ITT Analysis Set
- 20. Absolute Change (ANCOVA) from Baseline up to 2 years in WOMAC Pain Sub Score ITT Analysis Set
- 21. Absolute Change (ANCOVA) from Baseline up to 2 years in WOMAC Function Sub Score ITT Analysis Set
- 22. Repeat 16-21 for PP Analysis set
- 23. Concomitant Pain Medication by Treatment ITT Analysis Set

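### The SAP's medication-timing classes do not measure analgesic use at entry, yet they define the pain-medication subgroups and a baseline characteristic

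*SAP*

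**What the plan says.** SAP Section 14 sorts medications into Previous, Concomitant and Post-treatment. On the first class it says "Medications that start and stop prior to the date of first dose of study medication will be classified as previous medication". The second applies "If a medication starts or stops on or after the date of first dose of study medication and prior to last dose".

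Appendix 19.3 turns this into an ordered if / else-if / else rule. With complete dates, a start after last dose gives Post-treatment, and the remaining steps are "2) else if CMend Year/month/day < DoFD year/month/day => CM is Previous; (3) else CM is Concomitant". With a missing end date, no branch leads to Previous; where only the start year is known, for example, the step is "2) else if CMstart Year < =DoLD year => CM is Concomitant".

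The classes are then used in three places:
- Section 10 lists "Pain medications [classified for 3 timing groups defined in Section 14" among the subgroups, as Yes/No overall and by ATC group. Section 16.5 tabulates cartilage thickness, WOMAC, the walk test and JSW by the Section 10 subgroups.
- Section 13.3 includes among the baseline characteristics "All other attributes defined in subgroups analysis set in Section 10".
- Item 23 of the key efficacy tables (SAP 19.5.2, under WOMAC) is "Concomitant Pain Medication by Treatment ITT Analysis Set".

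Protocol 5.4 and 6.5.1 have analgesics withheld for at least five half-lives before the screening and baseline WOMAC. Afterwards paracetamol, NSAIDs and tramadol "may be resumed following randomization and continued as needed during the trial".

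**The concern.** Regular analgesic use on most days of the previous month is one of the routes to eligibility (Protocol 5.3.1, criterion 7). A drug used before entry, paused for the washout and then taken up again should therefore be a common pattern. The SAP has no class for it.

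Previous holds only records already closed at first dose. That can include drugs given up long before screening, and it leaves out any record still open. Concomitant mixes drugs carried over from before entry with drugs first started on treatment. Which label an entry user receives depends on whether the site closed the record for the washout, and neither document settles that.

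Three readings are at stake. The pain-medication line in the baseline table may not describe use at baseline. The Previous = No stratum, the natural pre-randomization subgroup for WOMAC, may contain current users. The concomitant pain-medication table cannot separate carry-over from new starts.

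**Working it through.** The plan gives no figure to reproduce on this point. The check has two parts: running test records through the rule, and showing how far Previous could depart from entry use under stated assumptions.

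**1. Labels.** First dose is day 1. Last dose is Week 80, day 80 × 7 + 1 = 561. The rule is SAP 19.3, using the complete-date and missing-end cells.

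| Record | Start day | End day | Label |
|---|---|---|---|
| Stopped before first dose | -200 | -5 | Previous |
| In use at entry, ongoing | -200 | missing | Concomitant |
| In use at entry, stops on treatment | -200 | 300 | Concomitant |
| In use at entry, stops after last dose | -200 | 700 | Concomitant |
| First started on treatment | 200 | missing | Concomitant |
| First started after last dose | 600 | missing | Post-treatment |
| Washout entered as a stop: old record | -200 | -3 | Previous |
| Washout entered as a stop: resumed record | 2 | missing | Concomitant |

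Rows 2 to 5 share one label although only row 5 is a new start. The last two rows are the same patient history as row 2 with the washout entered differently, and the labels change.

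**2. Previous against true entry use.** Let u be the share of subjects using an analgesic at entry and c the share of those whose record spans first dose. Assume one pre-dose record per subject and no former users. Neither u nor c is in the documents.

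Reported Previous = u(1-c). Entry users within Previous = No = uc / (1 - u + uc).

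| u | c | Previous shows | Entry users within Previous = No |
|---|---|---|---|
| any | 0 | u (no understatement) | 0% |
| 0.4 | 0.5 | 0.4 × 0.5 = 20% | 0.20 / 0.80 = 25% |
| 0.6 | 0.7 | 0.6 × 0.3 = 18% | 0.42 / 0.82 = 51% |
| 0.8 | 0.9 | 0.8 × 0.1 = 8% | 0.72 / 0.92 = 78% |

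In subjects, with 109 per group and u = 0.7, there are 109 × 0.7 = 76.3 entry users. Previous shows 76.3 of them at c = 0, 57.2 at c = 0.25, 19.1 at c = 0.75 and 3.8 at c = 0.95.

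**3. Carry-over against new starts in item 23.** Let b be the share using at entry, k the share of those who continue or resume, and s the share of the others who start an analgesic. The Concomitant share is bk + (1-b)s. Again all values are assumed.
- b = 0.7, k = 0.9, s = 0 gives 0.63 + 0 = 63%.
- b = 0.5, k = 0.9, s = 0.36 gives 0.45 + 0.18 = 63%.

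Two quite different patterns give the same entry. With b = 0.6 and k = 1, new starts of 10% and 20% among the others show as 0.60 + 0.04 = 64% and 0.60 + 0.08 = 68%: a ratio of 1.06 where the ratio of new starts is 2.0. This mixing does not depend on how the washout is entered, because a resumed record is Concomitant too.

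**The case against.** The case against has weight.

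- **The rule acts on records, not drugs.** One drug with a closed and a resumed record falls in two classes. A reader might infer that baseline analgesic use is certainly understated. The documents do not support that: withholding is mandatory before the baseline WOMAC, first dose follows the same day or up to 3 days later (Protocol 7.1.3.1), and changes in medication must be recorded. If sites enter the washout as a stop, c is near 0 and entry use is captured. This stands.
- **New starts are not invisible.** A reader might infer that they cannot be seen at all. Section 14 lists each category as well as summarizing it, Section 11 provides by-subject listings, and starts after last dose are labelled Post-treatment. What is missing is a summary that compares arms. This stands too.
- **The stakes are limited.** The trial is randomized, WOMAC is taken after washout, and its model adjusts for the baseline score. New analgesic use is not an endpoint. The pain-medication subgroups are descriptive, are not among the three priority subgroups, and use all three classes. It would go too far to say that the WOMAC comparison is confounded. Protocol 7.2 does ask for careful recording of analgesics at baseline, but the reason it gives is eligibility.
- **Some material is not available.** Section 19.5 lists only key outputs and the table shells are a separate document, so it cannot be claimed that balance between arms will never be checked.

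None of this gives the plan a variable for analgesic use at entry. Previous follows its own definition, but Sections 10 and 13.3 put it to a use that the definition does not serve. Under either way of entering the washout, one of the two classes misleads.

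**Conclusion.** The point holds in a limited form. The labels are exclusive per record. A continuing pre-entry analgesic cannot be told apart from an on-treatment start in any planned summary visible in the documents. If the washout is entered as a stop, the resumed drug looks like a new start. Previous is therefore not a measure of use at entry, and its content depends on an unstated data-entry convention, yet it feeds a baseline characteristic and a set of WOMAC subgroup tables.

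The size is unknown. Under the assumptions above it runs from no understatement (c = 0) to 8% shown against a true 80% (u = 0.8, c = 0.9). The documents give no basis for choosing a value in that range. The primary MRI analysis is unaffected, no formal inference rests on these subgroups, and the dates remain in the listings. The change is worth making because it is cheap and yields a properly pre-randomization subgroup, not because a main conclusion is at risk.

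**What to change.** Before unblinding, add two flags to SAP Section 14 and Appendix 19.3, derived from dates already collected:

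- **(a) Analgesic in use at entry:** started before first dose, and either not ended before screening (Visit 1a) or with the end date missing. Because subjects are asked to stop analgesics only after Visit 1a, this captures entry use whether or not the record was closed for the washout.
- **(b) Newly started on treatment:** started on or after first dose, excluding resumption after washout of a drug already flagged under (a).

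Use (a) for the pain-medication baseline characteristic in Section 13.3 and as the pain-medication subgroup in Section 10. Split item 23 of the efficacy tables into in use at entry and newly started. The existing three classes can stay for the general medication tables.

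The cost is some SAP wording, a small amount of programming and a rule for matching a resumed drug to its earlier record (for example by coded drug name). No new data are needed.

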19.4 Handling of TEAE timing

	AEstart	AEstart	AEstart Year	AEstart missing
	Year/Month/day	Year/Month		
AEend	(1) if AEstart	(1) if AEstart	(1) if AEstart	(1) if AEend
Year/Month/day*	Year/month/day >	Year/month >	Year > DoLD	Year/month/day <
	DoLD	DoLD year/	year => AE is	DoFD year/month/day
	year/month/day	month +1 => AE	Post; (2) else if	=> AE is Prior; (2) else
	+30 => AE is Post;	is Post; (2) else if	AEend	if AEend
	(2) else if AEend	AEend	Year/month/day	Year/month/day >=
	Year/month/day <	Year/month/day	< DoFD	DoFD year/month/day
	DoFD year/month/	< DoFD	year/month/day	=> AE is TEAE
	day => AE is Prior;	year/month/day	=> AE is Prior;	
	(3) else AE is TEAE	=> AE is Prior; (3)	(3) else AE is	
		else AE is TEAE	TEAE	
AEend	(1) if AEstart	(1) if AEstart	(1) if AEstart	(1) if AEend
Year/Month	Year/month/day >	Year/month >	Year > DoLD	Year/month < DoFD
	DoLD	DoLD year/	year => AE is	year/month => AE is
	year/month/day	month +1 => AE	Post; (2) else if	Prior; (2) else if AEend
	+30 => AE is Post;	is Post; (2) else if	AEend	Year/month>= DoFD
	(2) else if AEend	AEend	Year/month <	year/month => AE is
	Year/month < DoFD	Year/month <	DoFD	TEAE
	year/month => AE	DoFD	year/month =>	
	is Prior; (3) else AE is	year/month =>	AE is Prior; (3)	
	TEAE	AE is Prior; (3)	else AE is TEAE	
		else AE is TEAE		

	AEstart	AEstart	AEstart Year	AEstart missing
	Year/Month/day	Year/Month		
AEend Year	(1) if AEstart	(1) if AEstart	(1) if AEstart	(1) if AEend Year <
	Year/month/day >	Year/month >	Year > DoLD	DoFD year => AE is
	DoLD	DoLD year/	year => AE is	Prior; (2) if AEend
	year/month/day	month +1 => AE	Post; (2) else if	Year>= DoFD year =>
	+30 => AE is Post;	is Post; (2) else if	AEend Year <	AE is TEAE
	(2) else if AEend	AEend Year <	DoFD year => AE	
	Year < DoFD year =>	DoFD year => AE	is Prior; (3) else	
	AE is Prior; (3) else	is Prior; (3) else	AE is TEAE	
	AE is TEAE	AE is TEAE		
AEend missing	(1) if AEstart	(1) if AEstart	(1) if AEstart	TEAE
	Year/month/day >	Year/month >	Year > DoLD	
	DoLD	DoLD year/	year => AE is	
	year/month/day	month +1 => AE	Post; (2) else AE	
	+30 => AE is Post;	is Post; (2) else	is TEAE	
	(2) else AE is TEAE	AE is TEAE		

^{*}When end time of AE is collected both end date and end time of AE will be compared to date and time of first dose and if the AE ends before first dose then AE is Prior, else AE is TEAE.

If subject is not treated, then flags are blank. Assumption is DoFD and DoLD are not missing and complete for all treated subjects.

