7.4.1.3 Definition of the Adverse Event Reporting Period

The AE reporting period for safety surveillance begins when the subject is included into the trial (date of first signature of informed consent) and continues until the end of the trial's post-treatment extended follow-up phase, or until the subject's final trial visit in case of early withdrawal.

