17.1 Adverse Events

Adverse Events will be coded using latest version of MedDRA at the end of each of 2 reporting periods (2 year and 5 year analyses).

For 2 years analysis: Treatment-emergent adverse events (TEAEs) are defined as those adverse events that either start or worsen in severity on or after the date of first dose of study treatment (first injection) until 30 days from last dose of study treatment (last injection). Where dates are missing or partially missing, adverse events will be assumed to be treatment-emergent, unless there is clear evidence (through comparison of partial dates) to suggest that the adverse event started prior to the first dose of study treatment or after the subject's last treatment (+30 days). See appendix 20.4 for details.

For 5 years analysis: All AEs from the complete duration of the study will be summarized (but not TEAEs, as these are not relevant per definition above). There will be no summaries of TEAEs for the 5 years analysis only AE

Pre-treatment emergent adverse events, i.e. adverse events starting between date of informed consent and until date of first dose of study treatment will be tabulated separately.

Adverse events of special interest (AESI) will include the following:

Injection site reactions will be summarized by treatment group and PT. These will be identified using higher level term (HLT) "Injection site reactions".

Similarly, musculoskeletal complaints (eg. Back pain, neck pain), will be identified using prespecified SOC "Musculoskeletal and connective tissue disorders" and will be summarized by treatment group and by PT.

In addition, Neoplasms will be identified using pre-specified SOC "Neoplasms benign, malignant and unspecified (including cysts and polyps)" and will be summarized by treatment group and by PT.

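### SAP 19.4 flags a screening adverse event that is still open at first dose as treatment-emergent, although SAP 17.1 excludes it unless it worsens

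*SAP*

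**What the plan says.** SAP 17.1 uses onset or worsening as its criterion in three places.

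- **Definition (2-year analysis).** TEAEs are events that "either start or worsen in severity on or after the date of first dose of study treatment (first injection"), with the window running "until 30 days from last dose of study treatment (last injection").
- **Missing or partial dates.** An event is assumed treatment-emergent unless there is clear evidence to "suggest that the adverse event started prior to the first dose of study treatment", or that it began after the window closed.
- **Pre-treatment events.** These are also defined by onset: "adverse events starting between date of informed consent and until date of first dose of study treatment will be tabulated separately".

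Section 17.1 then refers to appendix 20.4 for details. The SAP has no such appendix; the table is in 19.4.

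SAP 19.4 is a grid of four levels of start-date completeness by four levels of end-date completeness. Where any part of the start date is known, it is compared with last dose only, to assign Post. Prior is assigned only when the end date falls before first dose. Everything left is a TEAE. The footnote for complete end dates and times says the same: "if the AE ends before first dose then AE is Prior, else AE is TEAE". No cell compares the start date with first dose, and none tests for worsening. Untreated subjects get a blank flag.

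Screening events will be in the database, because under Protocol 7.4.1.3 the AE reporting period "begins when the subject is included into the trial (date of first signature of informed consent").

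**The concern.** The two sections give different answers for the same event, and 19.4 is the one a programmer would code. An event with a known pre-dose onset can meet the 17.1 description of a pre-treatment event and also carry the TEAE flag from 19.4, so it can appear in both sets of tables.

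The screening period lasts 4 to 42 days and includes analgesic washout (Protocol 7.1.2), so events that begin there and are still open at the first injection are plausible. Counted as TEAEs, they add a background unrelated to treatment. It should be similar across randomized arms. It raises absolute incidence everywhere and makes the arms look slightly more alike, which is not the cautious direction when looking for harm. The tables mainly exposed are the overall, SOC/PT, severity, local/systemic and musculoskeletal TEAE tables, and the table of terms reaching 5% in any group.

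**Working it through.** **1. The rule followed through.** DoFD and DoLD are the days of first and last dose. Take a treated subject with DoFD = day 1 and, on schedule, DoLD = day 561 (560 days later, Week 80). With complete dates, Post requires start > 561 + 30 = 591, and Prior requires end < 1.

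| Event (no worsening) | Post? | Prior? | 19.4 | 17.1 |
|---|---|---|---|---|
| Start day -20, end day 5 | No | No | TEAE | Pre-treatment |
| Start day -20, end missing | No | Not tested | TEAE | Pre-treatment |
| Start day -20, end day -3 | No | Yes | Prior | Pre-treatment |

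**2. Why this is general.** If start < DoFD, then start < DoLD too, so the Post test always fails. If the end is on or after DoFD, or missing, the Prior test fails or is not applied. Only TEAE remains.

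A cell-by-cell enumeration agrees. It used three first-dose dates, onsets 42 to 1 days before first dose, all 16 combinations of date completeness, and ends on or after first dose or missing. All 79,380 combinations whose recorded start was clearly before first dose came out TEAE.

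Events that had in fact ended before first dose, with a complete start date, were Prior in all 2,709 cases with a complete end date and TEAE in all 2,709 with a missing one. These counts describe the grid, not expected trial frequencies.

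**3. Who is affected.** The affected events are in treated subjects, begin in screening and do not worsen. Those that worsen after dosing are TEAEs under 17.1 as well. Conditions already present at the initial visit that do not worsen are not AEs (Protocol 7.4.1.1).

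**4. Scale, by assumption.** Let b be the share of subjects with such an event. The documents give no value.

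| b | Of 545 | Per group of 109 |
|---|---|---|
| 2% | 10.9 | 2.2 |
| 5% | 27.3 | 5.5 |
| 10% | 54.5 | 10.9 |

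A subject who has another TEAE anyway does not add to the overall count.

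**5. Dilution, illustrated.** Suppose an AE class has true incidence 10% against 5%, and an independent background b in that class in both arms. Observed incidence is 1 - (1 - p)(1 - b), and the risk difference is 0.05 × (1 - b).

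| b in this class | Incidences | Ratio | Difference (points) |
|---|---|---|---|
| 0% | 10.0% v 5.0% | 2.00 | 5.00 |
| 2% | 11.8% v 6.9% | 1.71 | 4.90 |
| 5% | 14.5% v 9.75% | 1.49 | 4.75 |
| 10% | 19.0% v 14.5% | 1.31 | 4.50 |

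If b is the share of subjects with any open screening event, this table puts all of them into one class and is an upper bound. If one fifth fell in the class (again an assumption), b there is 0.4%, 1% or 2% and the ratios are 1.93, 1.83 and 1.71.

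**6. The 5% table.** With 109 per group, 5 subjects is 4.6% and 6 is 5.5%, so one misclassified subject can bring a term into the table.

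**The case against.** Three defences of the rule can be made.

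- **It is a cautious rule for incomplete dates.** This fails. The conflict arises in the cell where both dates are complete, and the incomplete-date rule in 17.1 itself turns on onset. It holds only for the column with a missing start date, where an end-date or default rule is reasonable.
- **The text of 17.1 governs.** It may, but it sends the reader to the appendix for details, and the appendix gives the rule to be programmed.
- **The consequences are small.** Much of this stands. TEAE summaries are numbers and percentages, with no planned test or ratio. The risk difference shrinks only by the factor (1 - b). Injection-site reactions to trial product cannot begin before the first injection. Events judged related, or leading to discontinuation, should rarely be non-worsening events that predate dosing. All SAEs are also tabulated regardless of emergence, and the AE listing shows onset dates.

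A reader might infer that every screening event becomes a TEAE, that all TEAE outputs are materially wrong, or that the safety comparison is biased toward one arm. The documents support none of these. Events with a complete end date before first dose are classed Prior, and those that worsen are rightly TEAEs. Several tables are barely touched, and the background should be similar across arms. A reader might also suppose that the logic was copied from the medication table in 19.3, where overlap with treatment is the right test. The logic matches, but the SAP does not say so.

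**Conclusion.** The contradiction is real: 19.4 gives a wrong classification by the SAP's own definition, even with complete dates. It applies to treated subjects with a non-worsening event that starts in screening and is open, or has no end date, at first dose. The effect is an over-count of TEAEs in all arms and a modest dilution of between-arm contrasts in descriptive tables.

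The size cannot be derived from the documents. The figures of 11, 27 and 55 subjects rest on assumed rates of 2%, 5% and 10%, and the ratios of 1.71, 1.49 and 1.31 are upper bounds for a single class.

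Three things are unaffected: AIRs, which are derived from diary pain and swelling (SAP 17.2.3); the 5-year summaries, which do not use the TEAE flag; and the efficacy analyses. It should be fixed because two incompatible definitions should not stand in one plan and the correction is cheap.

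**What to change.** In SAP 19.4, put a start-date test ahead of the others:

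1. If the start date, complete or partial but clearly earlier, is before first dose, classify the event as Prior unless worsening on or after first dose is recorded.
2. State how worsening is identified: a dated change in severity, or a new AE record for the worsened event. Say which of these the CRF captures. Protocol 7.4.1.2 asks for onset and resolution dates and severity but does not describe dated severity changes. Without this step, the new test could drop events that truly worsened.
3. Where worsening cannot be determined, keep the event as a TEAE or show it in a sensitivity table.
4. Where the start date is missing or cannot be ordered against first dose, keep the present end-date rule.

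Correct the pointer in 17.1 from appendix 20.4 to 19.4.

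The cost is SAP wording, a short change to the derivation code and a check of what the CRF records. The start-date test itself needs no new data. Whether worsening can be identified from the data already collected is not clear from the documents, which is why steps 2 and 3 belong in the same change.
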